6.8. Study size and feasibility

See appendix 4 (first feasibility matching on age, sex, comorbidity score) and appendix 5 (second feasibility matching on all predefined propensity score variables). Propensity score distribution plots with c-statistics are available in appendix 6. Table 1 showing prevalence of baseline characteristics and standardized differences in distribution are available in appendix 7.

7. Limitation of the methods

- Missingness in prognostic factors is a major challenge which is addressed in this emulation by multiple imputation using a non-parametric imputation algorithm. Multiple imputation usually assumes that missingness can be explained by observed characteristics, which may be empirically evaluated using principled missingness diagnostics, but the true underlying missingness mechanisms are usually unknown. Nevertheless, multiple imputation makes use of additional information (auxiliary covariates) which can render the underlying missingness assumptions more plausible. In addition, assumptions for alternative missing data approaches like complete case analysis or the "missing indicator approach" come with even stronger assumptions and additionally have the limitation of significantly reduced sample sizes, especially when comprehensively adjusting for known confounders and prognostic factors.
- Data continuity is a major challenge in EHR databases since "guaranteed" observable periods (such as continuous enrolment periods in administrative claims data) do not exist which may lead to measurement error in key covariates and exposure misclassification. Sensitivity analysis #8 tries to address this requiring patients to have had at least one visit before the index date which increases the likelihood that a patients was not only diagnosed at the respective center but is also regularly seen.
- Balancing patients on calendar year is not possible since calendar year shows instrumental variable-like behaviours (see Figure 13), i.e., it perfectly predicts treatment assignment and does not have any association with the outcome other than through the exposure. This assumption is formally untestable but clinically reasonable since there has not been any other significant change in treatment paradigms for FLAURA-like EGFR-mutated NSCLC populations other than introduction of osimertinib. The improvements of radiation of brain metastases may be the only exception, but it is expected that this may be of negligible significance for the scope of this emulation.

• Proportions of Asian race and patients with smoking history is different in the used US-only EHR-derived databases and the FLAURA trial population which can lead to altered treatment effect estimates since race was found to be an effect modifier in the trial's subgroup analyses. This limitation is address in sensitivity analysis #7 by re-weighting the distribution in these covariates to match that of the FLAURA populations.

8. Protection of human subjects

This study has been approved by the Brigham and Women's Hospital Institutional Review Board.

9. References

- 1. Jm F, A P, D M, et al. Nonrandomized Real-World Evidence to Support Regulatory Decision Making: Process for a Randomized Trial Replication Project. *Clin Pharmacol Ther*. 2020;107(4). doi:10.1002/cpt.1633
- 5. Soria Jean-Charles, Ohe Yuichiro, Vansteenkiste Johan, et al. Osimertinib in Untreated EGFR-Mutated Advanced Non–Small-Cell Lung Cancer. *N Engl J Med*. 2018;378(2):113-125. doi:10.1056/NEJMoa1713137

10.1. CONSORT diagrams

The following CONSORT attrition diagrams depict the process to select eligible FLAURA-like populations in EDB1, EDB2 and EDB4 for the main analysis, respectively.

Figure 6. CONSORT attrition to select eligible FLAURA-like populations in EDB1.

EDB1 attrition

[figure not shown]

Figure 7. CONSORT attrition to select eligible FLAURA-like populations in EDB2.

EDB2 attrition

[figure not shown]
[figure not shown]

Figure 8. CONSORT attrition to select eligible FLAURA-like populations in EDB4.

edb4 attrition

10.2. Covariate balance figures

The following figures illustrate the balance of key covariates included in propensity score models among eligible FLAURA-like populations in EDB1, EDB2 and EDB4, respectively.

Figure 9. EDB1 covariate balance of covariates included in propensity score model before and after matching.

[figure not shown]

Figure 10. EDB2 covariate balance of covariates included in propensity score model before and after matching.

[figure not shown]
[figure not shown]

[figure not shown]
Figure 11. EDB4 covariate balance of covariates included in propensity score model before and after matching.

10.3. Sample size/power calculations

Power estimations are computed based on the average number of observed events across imputed and matched datasets according to the methodology described by Schoenfeld.³⁵ Considering EDB1 only for primary analysis and assuming a HR = 0.8 and an alpha = 0.05 (2-sided), this results in an estimated statistical power (1-estimated type II error) of 80%.

Figure 12. Number of events needed to achieve x% power.

10.4. Additional Figures and Tables

Table 10. Lab measurement plausibility thresholds.

Lab and standardized unit	Lower plausibility threshold	Upper plausibility threshold
c_albumin_g_l	10	200
c_alp_u_l	1	2000
c_alt_u_l	1	90000
c_ast_u_l	1	90000
c_bilirubin_mg_dl	0.1	80
c_calcium_mg_dl	0.1	20
c_chloride_mmol_l	0.1	200
c_eosinophils_leukocytes_ratio	0	100
c_glucose_mg_dl	0.1	2000
c_granulocytes_leukocytes_ratio	0	100
c_hemoglobin_g_dl	0.1	20
c_ldh_u_l	0.1	Inf
c_lymphocyte_10_9_l	0	1e+06
c_lymphocyte_leukocyte_ratio	0	100
c_monocytes_10_9_l	0	1e+06
c_neutrophil_10_9_l	0	1e+06
c_platelets_10_9_l	0	5000
c_protein_g_l	1	300
c_urea_nitrogen_mg_dl	0.1	250

 Table 11. Vital sign measurement plausibility thresholds.

Vital sign	Lower plausibility threshold	Upper plausibility threshold
c_sbp	50	250
c_dbp	30	150
c_bmi	10	80
c_bsa	0.5	3.5
c_height	0.5	3
c_oxygen	50	100
c_pain	0	10
c_hr	20	250
c_resp	5	50
c_temp	86	113
c_weight	20	300

 Table 12. Mapping from State to Region.

State	Region
СТ	Northeast
ME	Northeast
MA	Northeast
NH	Northeast
RI	Northeast
VT	Northeast
DE	Northeast
NJ	Northeast
NY	Northeast
PA	Northeast
IL	Midwest
IN	Midwest
MI	Midwest
ОН	Midwest
WI	Midwest
IA	Midwest
KS	Midwest
MN	Midwest
МО	Midwest
NE	Midwest
ND	Midwest

SD	Midwest
FL	South
GA	South
MD	South
NC	South
SC	South
VA	South
DC	South
WV	South
AL	South
KY	South
MS	South
TN	South
AR	South
LA	South
OK	South
TX	South
AZ	West
CO	West
ID	West
MT	West
NV	West
NM	West

UT	West
WY	West
AK	West
CA	West
HI	West
OR	West
WA	West

Figure 13. Treatment initiation trends by calendar year and treatment in EDB1.

Treatment initiation trends in edb1

Treatment (0 = SoC, 1 = Osimertinib) - 0 - 1

[figure not shown]

Figure 14. Treatment initiation trends by calendar year and treatment in EDB2.

Treatment initiation trends in edb2

Treatment
$$(0 = SoC, 1 = Osimertinib) - 0 - 1$$

[figure not shown]

Figure 15. Treatment initiation trends by calendar year and treatment in EDB4.

Treatment initiation trends in edb4

Treatment (0 = SoC, 1 = Osimertinib) - 0 - 1

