6.6.7. Context and rationale for covariates

We identified a series of covariates that are strong prognostic factors for the outcome and auxiliary covariates which may be useful to impute missing data. Such covariates comprise demographics, covariates indicating disease-severity, cancer-specific covariates as well as pathological and genetic factors. In addition, selected labs and vitals are considered since they were shown to carry a high amount of prognostic information as described in Becker, Weberpals, et al.¹⁰ For these variables, additional plausibility checks and transformations are carried out. In detail, labs and vitals are individually checked if they cross a certain biologically implausible threshold (e.g., a heart rate of 0) in which cases the values are set missing and imputed in a next step. These thresholds were compiled by experienced practicing physicians and medical oncologists and are listed in appendix **Table 10** and **Table 11**.

Note that not all covariates are available across all databases used for this trial emulation. In the analytical stage, the most comprehensive model will be fit for each database individually.

Table 5. Operational definitions of key covariates used for trial emulation.

Characteristic	Harmonized analysis variable name	R function to derive covariate (see pdf in appendix)	Details ¹	Variable encoding	Assessment window
Age at initial diagnosis	dem_age_initial_diagnosis	edbx_get_demographics()	Age measured at initial diagnosis of eligible primary tumor	Nominal (<60, 60-69, 70-79, 80+)	[-inf;0] at initial diagnosis of primary cancer
Age at index date	dem_age_index	edbx_get_demographics()	Age measured at index date	Binary (<60, 65+); modelled continuously in ROPRO ¹⁰	[0;0]
Sex	dem_sex	edbx_get_demographics()	Sex	Binary (Male, Female)	[0;0]
Year of index date	c_year_index	De novo derived from dt_index	Calendar year in which patient initiated study treatment	Nominal (<2018, 2018+)	[0;0]
Family history	dem_family_history	edbx_get_demographics()	Family history of cancer	Logical (TRUE, FALSE)	[0;0] (no specific date is associated)
Race	dem_race	edbx_get_demographics()	Race categorized as in the original RCT	Binary (Asian vs non-Asian)	[0;0]
Ethnicity	dem_ethnicity	edbx_get_demographics()	Ethnicity	Hispanic, Non-Hispanic	[0;0]
Region	dem_region	edbx_get_demographics()	US region patient receives care in; if given on a state level, region is manually mapped (see	Nominal (Northeast, South, West, Midwest)	[0;0]

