6.7. Data analysis

6.7.1. Context and rationale for analysis plan

To emulate the FLAURA trial, the following analytical workflow will be used (Figure 4). First, an analytical cohort with covariates on key eligibility criteria and prognostic factors will be derived across all databases. To ensure reproducibility and consistency throughout the entire ENCORE project, the internally developed *encore.io* R package streamlines this process using the functions referenced in Table 5. Operational definitions of key covariates used for trial emulation. Table 5 (code documentation see appendix). The analytical cohort will be derived by first identifying an advanced NSCLC inception cohort of initiators of osimertinib, erlotinib or gefinitib in the first line setting as described in section 6.6.4. Next, key eligibility criteria will be applied in which patients with missing values are considered eligible in the respective attrition steps to allow thorough missing data investigations.

² For calculation of ROPRO prognostic score¹⁰, this variable is log transformed.

³ For calculation of ROPRO prognostic score¹⁰, this variable is log-log transformed.

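### Table 10 keeps 1000-fold unit errors in three white-cell counts, and its lower limits let some ROPRO inputs take values whose log, ratio or log-log is not finite

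*Protocol*

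**What the plan says.** Section 6.6.7 states that labs and vitals are "individually checked if they cross a certain biologically implausible threshold". Values that do so become missing and are imputed afterwards. Practising physicians and oncologists compiled the limits, which are in Tables 10 and 11 (section 10.4).

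The relevant rows of Table 10, each giving variable, lower limit and upper limit, are:

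- "c_lymphocyte_10_9_l 0 1e+06"
- "c_monocytes_10_9_l 0 1e+06"
- "c_neutrophil_10_9_l 0 1e+06"
- "c_platelets_10_9_l 0 5000"
- "c_eosinophils_leukocytes_ratio 0 100"

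The lymphocyte/leukocyte ratio also runs from 0 to 100, and LDH from 0.1 to infinity.

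Footnote 2 to Table 5 says that, for the ROPRO score, "this variable is log transformed". The footnote marks monocytes, eosinophils/100 leukocytes, the lymphocyte/leukocyte ratio and the neutrophil/lymphocyte ratio (NLR), among others. Footnote 3 gives LDH a log-log transform. Table 5 computes NLR as neutrophils divided by lymphocytes. Sensitivity analysis #1 (Table 9) matches on ROPRO instead of the propensity score.

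**The concern.** A plausibility filter is useful only if its limits lie near the edge of what can occur. For three white-cell counts the upper limit is so high that the commonest type of gross laboratory error, a count per microlitre stored as 10^9/L, stays well inside it. A few such values can dominate the variance of a covariate that is used as continuous. The covariate then carries almost no weight in a propensity model, and its standardized difference shrinks because the denominator has grown. Section 6.7.1 makes the Cox model conditional on sufficient balance, judged by ASMDs, so a masked ASMD would matter.

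The lower limits raise a separate, narrower issue. Some variables that ROPRO logs, or uses in a ratio that it logs, may be exactly 0. LDH may take values at which its log-log is undefined. One such value makes that patient's score non-finite.

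**Working it through.** **Inputs.** The limits are from Table 10, and the transforms and the NLR formula from Table 5 and its footnotes. The typical counts below are assumptions; the protocol gives none.

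**1. Upper limits.** A 1000-fold error is removed only if true count × 1000 > upper limit, that is, if true count > limit / 1000.

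| Count (10^9/L) | Assumed typical | × 1000 | Upper limit | Result |
|---|---|---|---|---|
| Lymphocytes | 0.5–5 | 500–5,000 | 1,000,000 | kept |
| Monocytes | 0.1–1.5 | 100–1,500 | 1,000,000 | kept |
| Neutrophils | 1–20 | 1,000–20,000 | 1,000,000 | kept |
| Platelets | 100–450 | 100,000–450,000 | 5,000 | removed |

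For the three white-cell counts the true value would have to exceed 1,000,000 / 1000 = 1000 × 10^9/L before the error was caught. Even a 10,000-fold error passes throughout these ranges (the largest is 20 × 10,000 = 200,000). The white-cell limit is 1,000,000 / 5000 = 200 times the platelet limit in the same unit.

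**2. What such errors would do.** Assume lymphocytes are lognormal with median 1.5 and log-SD 0.4. The mean is 1.5 × exp(0.4²/2) = 1.62 and the SD is 0.68. If 1% of values are 1000-fold too high, the mean becomes 1.62 × (0.99 + 0.01 × 1000) ≈ 18 and the SD about 170 to 175.

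For the effect on balance, simulate n = 3000 with 30 datasets per error share, and a logistic treatment model with coefficient 0.5 per SD of the true count:

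- No errors: coefficient 0.50, ASMD about 0.47.
- 0.2% errors (0.002 × 3000 = 6 values): coefficient 0.02 or less, ASMD about 0.03, while the ASMD of the true values is still about 0.47.
- 0.5% to 2% errors: coefficient about 0.

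The error share, the true imbalance, and the linear entry of the raw count are all assumptions.

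**3. Lower limits against the transforms.** Footnote 2 marks 13 variables, of which 12 have a row in Table 10 or 11. Nine of those have a lower limit above 0: ALP, ALT, bilirubin, calcium, glucose, urea nitrogen, systolic blood pressure, BMI and heart rate. Three allow 0: eosinophils/100 leukocytes, lymphocyte/leukocyte ratio and monocytes. The thirteenth, NLR, has no row, and both of its components allow 0. A value equal to the limit does not cross it, so a zero is kept.

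- log(0) = −∞ for the three variables.
- NLR with lymphocytes 0 is infinite. With both counts 0 it is undefined. With neutrophils 0, log(NLR) = −∞.
- LDH: log(log(x)) is undefined for 0.1 ≤ x < 1 and −∞ at x = 1. For comparison, it is −4.61 at 1.01 and 1.67 at 200.

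**The case against.** Several stronger readings are tempting, and the document does not support them.

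- *Table 10 as a whole fails.* The unit-error point concerns 3 of 19 rows, and the platelet row works.
- *The check exists because unit errors are expected.* The only example in section 6.6.7 is a heart rate of 0. The Table 10 header refers to standardized units, so conversion may already have happened in the laboratory function, whose documentation is not shown. On the other side, Table 5 names glucose in mg/dL but describes it in mmol/L, names hemoglobin in g/dL but describes it in g/L, and names urea nitrogen in mg/dL but describes it in mg/L. Unit slips are therefore not far-fetched, but these are mismatches of description, not evidence of wrong data.
- *The primary analysis is confounded.* The text at hand does not list the propensity-score covariates, and Figure 9 is not shown. Section 6.6.7 promises the most comprehensive model for each database, so entry of these counts is possible but not established. Lymphocytes and neutrophils are described as used to compute NLR, where an equal unit error in both cancels.
- *The zeros harm the primary analysis.* The log applies only to ROPRO, which is the matching variable only in sensitivity analysis #1, and Table 9 calls that analysis experimental.
- *The ROPRO caliper has no defined standard deviation.* The SD-based caliper in section 6.7.1 is for the propensity score. No scale is stated for the ROPRO caliper.

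It is also fair to say that a recorded zero, for instance for eosinophils, can be real, and that a filter which keeps it is working properly. A rule for zeros may sit in code or in an analysis plan not shown. These points limit the reach of the concern. They do not make 1,000,000 × 10^9/L a plausible count, or make the LDH limit of 0.1 compatible with a log-log transform.

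**Conclusion.** The point holds for specific rows and is minor. The upper limits for lymphocytes, monocytes and neutrophils do not serve the purpose that section 6.6.7 gives them: every 1000-fold error in a typical value is kept. Whether this changes any result depends on two things the protocol does not show: whether such errors survive unit standardization, and whether these counts enter the imputation or propensity models. If both are so, a share as small as 0.2% is enough, in the simulation, to hide a large imbalance. That is an illustration of sensitivity, not an estimate for this study.

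The lower limits for the logged or ratio inputs and for LDH can give a non-finite ROPRO score. That affects sensitivity analysis #1 only.

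**What to change.** 1. Ask the same clinical panel to set a separate upper limit for each of the three white-cell counts, low enough to catch a 1000-fold error in a typical value. A common limit of 1000 × 10^9/L would not do, because an error passes whenever the true count is below 1000 / 1000 = 1.0. Under the lognormal above that is Φ(ln(1/1.5)/0.4) ≈ 16% of lymphocyte values, and it covers most of the assumed monocyte range of 0.1–1.5. Limits for monocytes and lymphocytes need to be well below 1000.
2. Keep genuine zeros, and state a fixed small offset or floor applied before the log and ratio steps of ROPRO. Do not raise the lower limits of these variables above 0. That would delete real values because of their own size, which is the missingness mechanism that section 6.7.1 names as leading to critical bias.
3. Raise the LDH lower limit above 1 U/L so that the log-log is defined. Because the transform falls steeply just above 1, the panel may prefer a limit clearly higher than that.

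The timing needs no change, since the check already precedes imputation. The cost is four cells of Table 10 and one sentence on zeros. The downside is that a very few true extreme values would be set to missing and imputed.
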